9.2.1 Missing data

Efficacy

No imputation will be done on missing efficacy data.

Safety

No imputation will be done on missing safety data, unless otherwise stated below

Dates

Dates of remote events (e.g. AEs or concomitant medication) may be partially incomplete, as the day and/or month may be unknown. AEs with incomplete start dates will be considered as

treatment emergent, only if they are definitely known to have started after randomization. For treatment, emergent AEs with incomplete start dates (unknown date and known month), the start date will be taken as the first of the corresponding month or date of randomization, whichever is later. Incomplete dates for concomitant medications will not be imputed.

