3.1.6 Discontinuation Criteria

1. Subjects are free to drop out from the study at any time without stating any reason and they can choose not to receive the drug or equivalent after signing the consent. If the subject chooses not to receive the study drug after signing the consent, the subject must notify the Investigator before dispensing of the study drug. However, the subjects will continue to receive all the standard medical care, to which they are entitled.
2. Investigators may also, at their discretion, withdraw the subject from participating in the study at any time, with prior notification to the sponsor with the reason for the same.

However, subjects must be withdrawn from therapy, if any of the following events occur after giving the consent:

- a. Subject suffers from significant intercurrent illness or undergoes surgery during the course of the study where continued participation in the study presents a significant safety concern.
- b. Subject develops anti-epoetin antibodies or PRCA or severe allergic reaction
- c. Subjects requires epoetin dose more than 300 IU/kg/week
- d. Subject experiences adverse event or laboratory abnormality, when withdrawal would be in the best interest of the subject, as assessed by the investigator
- e. The subject fails to comply with the requirements of the protocol (e.g., visit window deviation) the subject may be withdrawn at the discretion of investigator and/or after discussion with medical monitor.
- f. It is necessary to further protect the health of the subject or the integrity of the study.
- g. Pregnancy.

3. The study is terminated by Sponsor, Regulatory Authorities or IEC/ IRB.

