9 STATISTICAL METHODS

9.1 Analysis Sets

Three cohorts will be considered for the analysis: The modified intention-to-treat (mITT) cohort, per protocol (PP) and safety cohort. Per-Protocol cohort population will be considered as primary population for analysis of efficacy.

Modified Intention-to-treat Cohort:

All randomized subjects who receive study medication, have a baseline and at least one post-treatment measurement will be included in the MITT Cohort.

Per-protocol Cohort:

All randomized subjects who complete both the baseline visit and end of treatment visit and who have no major protocol violations will be included in the PP population. Subjects with major protocol violations will be excluded from this cohort.

Detailed description of what constitutes a protocol violation will be defined in the SAP.

Safety Cohort:

All subjects who are randomized at baseline visit will be included in the safety analyses for safety endpoints.

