9.2 General Statistical Considerations

Analysis for all efficacy endpoints using the PP population will be the primary approach for analysis. Secondary analysis will be performed using the mITT population. For safety endpoints using the safety cohort will be the primary approach for analysis.

The SAS® package (SAS® Institute Inc., USA, and Version 9.2 or higher) will be used for statistical evaluation.

Descriptive statistics, such as mean, standard deviation, median, minimum and maximum values will be provided for the continuous variables and the number of observations and percentage will be provided for the categorical variables.

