9.8 Sample Size Determination

A sample size of 112 subjects per group is calculated to achieve a power of more than 80% for proof of equivalence for both co-primary endpoints. Considering 2 stratification factors i.e. body weight (Kg): ≤ 58 , $59-74$ & ≥ 75 , Hb level (g/dl): $10 - 11$ & $> 11 - 12$ and to balance between the two treatment groups in Thailand and Russia, the total number of subjects to be randomized is estimated to be 264 (n=132 subjects in each group) since a drop-out rate of approximately 18% was expected.

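### With no imputation and a single 6-month change-score ANCOVA, the mITT analysis is no check on dropout before month 6, and that dropout is informative for the dose co-primary

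*Protocol*

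**What the plan says.** Protocol Section 9.1 makes the per-protocol set primary: "Per-Protocol cohort population will be considered as primary population for analysis of efficacy". That set takes in "All randomized subjects who complete both the baseline visit and end of treatment visit and who have no major protocol violations". Section 9.2 gives the mITT set the supporting role: "Secondary analysis will be performed using the mITT population". Entry to it is broad: "All randomized subjects who receive study medication, have a baseline and at least one post-treatment measurement will be included in the MITT Cohort". A 6-month value is not required.

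Section 9.4.1 names one model for each co-primary endpoint: an ANCOVA of the change from baseline to 6 months, with center, Hb level and weight as covariates. The 95% confidence interval is compared with ±0.5 g/dl for haemoglobin and ±45 IU/kg/week for dose. Section 9.2.1 adds: "No imputation will be done on missing efficacy data".

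Section 3.1.6 lists events after which withdrawal from therapy is mandatory, among them "Subjects requires epoetin dose more than 300 IU/kg/week". Section 4.2.1 repeats this trigger for randomized subjects. Section 4.2.2 asks for the last scheduled assessments at withdrawal but does not provide for a later 6-month value. Section 4.2.3 rules out replacement. Section 9.8 sets 264 randomized subjects "since a drop-out rate of approximately 18% was expected".

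**The concern.** In an equivalence trial the second analysis set is there to show whether the per-protocol result depends on who was left out. Here the broad mITT definition suggests that early dropouts are covered, but the model and the missing-data rule take them out again.

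For the dose co-primary the loss is not neutral. The endpoint is change in IU/kg/week, and the withdrawal trigger is a level of the same quantity. Subjects who reach it before month 6 have among the largest increases, and neither model counts them. If they are more frequent in one arm, the estimated dose difference shrinks towards zero, which favours the equivalence claim. The interim analysis in Section 9.6 follows the same methods and supports a registration report, so it inherits the gap.

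**Working it through.** **Who enters each model.** I take Visit 16 (week 36) as the 6-month visit, because Section 9.6 ties the 24-week equivalence analysis to it.

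| Subject | PP model | mITT model |
|---|---|---|
| Lost before the 6-month visit | out | in the set by definition, out of the model (no change score, no imputation) |
| Has a 6-month value, major violation | out | in |
| Leaves after month 6 | out if the end of treatment visit means Visit 23 (week 64), as the heading of Section 6.5 suggests | in |
| Completes without major violation | in | in |

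The two models differ in rows 2 and 3 but share the gap in row 1.

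**The plan's own figure (Section 9.8).** 112 × 1.18 = 132.16, which gives the stated 132 per group and 264 in total.

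**How many subjects row 1 could hold.**
- Upper bound, all planned dropout before month 6: 0.18 × 264 = 47.5, about 48 (about 24 per arm).
- If 18% is a whole-study rate with constant hazard (assumption), the exposed time is week 13 to 36 out of week 13 to 64, that is 23 of 51 weeks. Loss = 1 − 0.82^(23/51) = 8.6%, and 0.086 × 264 ≈ 23.

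**Bias in the dose difference.** Let p be the excess fraction withdrawn for dose need in one arm, and let their change exceed the mean change of those remaining by D. The completer mean in that arm is too low by p × D. I take the mean change of those remaining as 0.
- p = 0.03 (about 4 of 132) and D = 100 to 200 (assumptions): 0.03 × 100 = 3 and 0.03 × 200 = 6 IU/kg/week. Against the margin, 3/45 = 7% and 6/45 = 13%.
- A subject who passes the limit has D of more than 300 minus the baseline dose. Baseline doses are not stated, so I vary them:

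| Assumed baseline (IU/kg/week) | Smallest D | p = 0.05 | p = 0.10 | p that hides all 45 |
|---|---|---|---|---|
| 75 | 225 | 11.2 | 22.5 | 20% |
| 120 | 180 | 9.0 | 18.0 | 25% |
| 180 | 120 | 6.0 | 12.0 | 37.5% |

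**Missingness in general.** With 18% missing in both arms, shifting the estimate by a full margin needs an arm difference among the missing of 0.5/0.18 = 2.8 g/dl or 45/0.18 = 250 IU/kg/week.

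**Whether data exist to do better.** Sections 6.4 and 7 schedule a blood count, post-dialysis body weight and dose review at each of Visits 9 to 16, with haemoglobin and the required dose recorded. A subject withdrawn for rising dose need therefore usually leaves a dose history, which the single-visit ANCOVA does not use.

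**The case against.** The strongest case on the other side has five parts.

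- **The two sets are not the same.** A reader might infer that mITT collapses into PP and adds nothing. The documents do not support that: mITT restores major violators and, if the end of treatment visit is week 64, everyone who leaves after month 6.
- **The 18% is not a month-6 figure.** Section 4.2.3 counts as dropouts those who do not complete the study. A reader might infer that 48 subjects will be missing, but 48 is only a ceiling.
- **Other outputs would show an imbalance.** Section 4.2.2 requires reasons for withdrawal in the final report. Mean haemoglobin and dose every 4 weeks are secondary endpoints, to which early dropouts contribute until they leave. This stands. It makes an imbalance visible but does not give an equivalence estimate that accounts for it.
- **Early withdrawals for dose need may be few, and balanced.** Screening excludes subjects above the same limit, and randomization requires a stable dose. Under the 25% steps in Section 5.1.7, a subject starting at 100 IU/kg/week (assumed) needs five increases to pass 300 (100 × 1.25^5 = 305). A reader might infer bias towards equivalence in every case. That does not follow: with balanced withdrawals there is little or no bias, and the smaller sample widens the interval, which works against the claim.
- **The SAP may add sensitivity analyses.** It is not at hand, so nobody can say that none exist. However, the protocol itself fixes the combination of no imputation and a single change score, so this is a stated choice and not a detail left open.

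**Conclusion.** The point holds for dropout before the 6-month assessment. For those subjects the mITT analysis has the same gap as the per-protocol analysis and cannot act as a check on it. The number affected is at most about 48 of 264, and about 23 under a constant hazard over the whole study.

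For the dose co-primary the loss is informative, because the withdrawal trigger is the endpoint quantity itself. Bias arises only if such withdrawals differ between arms. On the assumptions shown it is about 3 to 6 IU/kg/week for a 3-point excess, and about 6 to 22 for an excess of 5 to 10 points, against a margin of 45. The excess fractions, dose changes and baseline doses are all assumptions.

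A reader might infer that the equivalence conclusion is unsafe in general. The figures do not show that: hiding the whole margin needs an excess of 20% or more, so a comfortable result would stand. The gap matters mainly when a confidence limit lies near the margin. It deserves correction because a better analysis of data already collected is available at little cost.

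**What to change.** For the mITT analysis of both co-primary endpoints, replace the single-visit ANCOVA with a mixed model for repeated measures. Use all scheduled haemoglobin and weekly-dose values from Visit 9 to Visit 16, the same covariates, and treatment, visit and treatment-by-visit terms. Take the treatment contrast at the 6-month visit and compare it with the existing margins. State in the text which visit is the 6-month visit. The mixed model imputes nothing, so it agrees with Section 9.2.1.

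Add one sensitivity analysis of the dose endpoint that keeps subjects withdrawn for exceeding the dose limit, with their last recorded dose requirement. This assigns a 6-month value, so Section 9.2.1 needs one sentence allowing it as a sensitivity analysis.

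The cost is a short change of wording and a little more programming, with no new data or visits. The mixed model assumes data missing at random, which is doubtful for withdrawals driven by dose need, and the sensitivity analysis is needed for that reason. The primary per-protocol analysis and all clinical rules stay as they are, so the primary decision still excludes early withdrawals. What improves is the analysis meant to check it. Section 1.5.3 allows such a change by protocol amendment or in the SAP. It should be made before the unblinded analysis after Visit 16.

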6.4 Treatment Period (Week 14/Day 98 to Week 64/Day 448)

The study treatment period will be for 52 weeks. The subject will receive either EPIAO or EPREX one to three times a week at the end of dialysis session. During the treatment period, the subject will be instructed to visit the study facility one to three times a week on week 14/Day 98, week 15/Day 105, week 16/Day 112, week 20/Day 140, week 24/Day 168, week 28/ Day 196, week 32/Day 224, week 36/Day 252, week 40/Day 280, week 44/Day 308, week 48/Day 336, week 52/Day 364, week 60/Day 420 and week 64/Day 448 following randomization for study assessment.

The following assessments will be performed;

Visit 9: Week 14/Day 98 \pm 2 days

- Demographic data (body weight: post hemodialysis)
- Vital signs
- Physical examination
- Adverse events
- Concomitant medication
- CBC

- Dose adjustment if required as per section 5.1.7

Visit 10: Week 15/Day 105 ± 2 days

- Demographic data (body weight: post hemodialysis)
- Vital signs
- Physical examination
- Adverse events
- Concomitant medication
- CBC
 - Reticulocyte count

Dose adjustment if required as per section 5.1.7

Visit 11: Week 16/Day 112 ± 2 days

- Demographic data (body weight: post hemodialysis)
- Vital signs
- Physical examination
- Adverse events
- Concomitant medication
- CBC
- Iron study
- Immunogenicity testing for anti-EPO antibody
- Dose adjustment if required as per section 5.1.7

Visit 12: Week 20/Day 140 ± 2 days

- Demographic data (body weight: post hemodialysis)
- Vital signs
- Physical examination
- Adverse events
- Concomitant medication
- CBC
- Dose adjustment if required as per section 5.1.7

Visit 13: Week 24 /Day 168± 2 days

- Demographic data (body weight: pre and post hemodialysis)
- Vital signs
- Physical examination

- Adverse events
- Concomitant medication
- CBC
- Iron study
- BUN (pre and post hemodialysis)
- Immunogenicity testing for anti-EPO antibody
- Adequacy of dialysis measurement by Kt/V formula
- Dose adjustment if required as per section 5.1.7

Visit 14: Week 28/Day 196 ± 2 days

- Demographic data (body weight: post hemodialysis)
- Vital signs
- Physical examination
- Adverse events
- Concomitant medication
- CBC
- Dose adjustment if required as per section 5.1.7

Visit 15: Week 32/Day 224 ± 2 days

- Demographic data (body weight: post hemodialysis)
- Vital signs
- Physical examination
- Adverse events
- Concomitant medication
- CBC
- Dose adjustment if required as per section 5.1.7

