After informed consent during screening any clinically significant abnormality which meets the definition of AE should be recorded as a pre-treatment AE prior to the use of the product (Day 1) and should be recorded accordingly. Any new clinically significant event or worsening of existing medical history condition, which meets the definition of AE prior to the application of IP will also be considered as pre-treatment adverse event.

Post-treatment Adverse Events

All AEs recorded after the first dose of IP (Day 91) till the end of treatment will be considered as post-treatment AEs. Disease signs, symptoms and/or laboratory abnormalities already existing prior to the use of the product will not be considered as adverse experiences after treatment (post-treatment AEs) unless they reoccur after the subject/patient has recovered from the pre-treatment condition or they represent an exacerbation in intensity or frequency or the character of the condition worsens during the study period.

General Physical Examination Findings

At screening, any clinically significant abnormality should be recorded as a pre-existing condition. At the end of the study, any new clinically significant findings/abnormalities that meet the definition of an adverse event must also be recorded and documented as an adverse event.

Post-study Adverse Event

At the last scheduled visit, the investigator should instruct each subject to report any subsequent event(s) that occur within 14 days after discontinuation of treatment. The investigator should notify the sponsor of any death or adverse event occurring at any time after a subject has discontinued or terminated study participation that may reasonably be related to this study.

Abnormal Laboratory Values

A clinically significant laboratory abnormality should be documented as an adverse event if any one of the following conditions is met:

- The laboratory abnormality is not otherwise refuted by a repeat test to confirm the abnormality
- The abnormality suggests a disease and/or organ toxicity, then the underlying condition should be captured as an AE.
- The abnormality is of a degree that requires active management; e.g. change of dose, discontinuation of the drug, more frequent follow-up assessments, further diagnostic investigation, etc.

Lab abnormalities found during the screening tests will not be considered as adverse event.

Hospitalization, Prolonged Hospitalization or Surgery

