9.5.1 Adverse Event Analyses

All adverse events will be summarized in terms of severity, relation to study treatment, duration, action taken and subjects outcome. The number and the proportion of subjects who experienced AEs will be computed by treatment group, classified by Medical Dictionary for Regulatory Activities (MedDRA) Primary System Organ Class and Preferred Terms.

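### A partially dated AE is treatment emergent only on definite proof of onset after randomisation, so doubtful events around the switch lose the label

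*Protocol*

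**What the plan says.** Protocol section 9.2.1 (Dates) accepts that AE dates "may be partially incomplete, as the day and/or month may be unknown". It then gives two rules.

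- Rule 1 (class): an AE with an incomplete start date is "treatment emergent, only if they are definitely known to have started after randomization".
- Rule 2 (date): for treatment-emergent AEs with the day unknown and the month known, "the start date will be taken as the first of the corresponding month or date of randomization, whichever is later".

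No date rule is given for an unknown month. The general statement just above is "No imputation will be done on missing safety data, unless otherwise stated below", so these two rules are the only exceptions for AE dates.

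Three other places bear on the point. Section 9.5.1 states "All adverse events will be summarized in terms of severity, relation to study treatment, duration, action taken and subjects outcome", by treatment group and without restriction to treatment-emergent events. Section 8.1.1.2 uses a different term and a different anchor, the first dose and not randomisation: "All AEs recorded after the first dose of IP (Day 91) till the end of treatment will be considered as post-treatment AEs". Section 6.4 gives the length of exposure: "The study treatment period will be for 52 weeks".

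**The concern.** Every subject receives EPREX for at least 3 months before randomisation (section 3.1.2), and AEs are recorded from consent (section 8.1). Only a split at randomisation separates events under common EPREX treatment from events under the randomised product. The treatment-emergent label is that split.

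Rule 1 resolves doubt by withholding the label. The events most exposed are those in the calendar month of the switch from EPREX to EPIAO, where a switch effect would first appear. Rule 2 offers the randomisation date as a possible start date, which suggests that events in the randomisation month were expected to count. Under Rule 1, read on dates alone, they do not.

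Safety of the 1:1 conversion is part of the primary objective (section 2.1.1), and the interim report, which includes safety, is to support registration (section 9.6).

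**Working it through.** The protocol gives no figure here, so there is none to reproduce. The check has two parts.

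**1. Do the two rules fit together?** Take each of 365 randomisation dates in a year with each AE month from the randomisation month to 12 months later: 365 × 13 = 4,745 combinations.

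- Rule 2 selects the randomisation date only when it is later than the first of the AE month. This occurs only in the randomisation month, and not when randomisation falls on the 1st: 365 − 12 = 353 combinations.
- Rule 1, on date parts alone, is met only when the first of the AE month is later than the randomisation date.
- The two conditions exclude each other: 0 of the 353 combinations satisfy Rule 1.

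So on date parts alone the randomisation-date branch of Rule 2 has no cases. It has cases only if evidence beyond the date field may establish timing.

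**2. How much follow-up is affected?** Assumptions: randomisation dates uniform over a 365-day year, a constant AE rate, and full follow-up of 52 × 7 = 364 days.

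*Day missing, month known.* In a month of n days, randomisation on day d leaves n − d on-treatment days in that month. Summed over d this is n(n − 1)/2.

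- Year total: 7 × 465 + 4 × 435 + 378 = 5,373.
- Mean: 5,373 / 365 = 14.7 days (range 0 to 30).
- For the first 28 days, months with 29 or 30 remaining days are capped at 28. This removes 7 × 3 + 4 × 1 = 25 days, giving 5,348 / 365 = 14.65.

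*Day and month missing.* With randomisation i days after 1 January, 364 − i days of the year remain. The affected part of a window of F days is the mean of min(364 − i, F) over i = 0 to 364. For F = 364 this is (364 × 365 / 2) / 365 = 182 days.

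| Window after randomisation | Day missing | Day and month missing |
|---|---|---|
| 28 days | 14.65 / 28 = 52% | 96% |
| 168 days (24 weeks, the interim period in section 9.6) | 14.72 / 168 = 8.8% | 77% |
| 182 days (26 weeks) | 14.72 / 182 = 8.1% | 75% |
| 364 days (52 weeks) | 14.72 / 364 = 4.0% | 182 / 364 = 50% |

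These are shares of on-treatment AEs with incomplete dates, not of all AEs. The protocol does not say how many AEs will have incomplete dates. If 5% to 10% do (an assumption), the share of all on-treatment AEs affected over 52 weeks is:

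- all lacking only the day: 0.05 × 4% = 0.2% to 0.10 × 4% = 0.4%;
- all lacking the month too: 0.05 × 50% = 2.5% to 0.10 × 50% = 5%.

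**What reversal would let in.** The days of the randomisation month before randomisation number d − 1, with the same sum n(n − 1)/2, so they also average 14.7 days. For day-missing AEs, reversal admits about as many EPREX titration days as it regains on-treatment days, before stop dates and visit records are used.

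**The case against.** A reader might infer that the two rules contradict each other. The text does not support that. Rule 2 applies only to AEs that have passed Rule 1, and it sets a date, not a class. Both can be carried out in order.

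Nor does Rule 1 say that only the date field counts. AEs are recorded at Visit 8 (section 6.3) and again at Days 98, 105 and 112 (section 6.4). An AE absent at Visit 8 and first reported at Visit 9 could be known to follow randomisation without a recorded day, and Rule 2 would then give it the randomisation date. This stands. What remains is that the standard of proof is undefined, and that without such evidence the branch has no cases.

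A reader might also infer that events are dropped from the safety analysis. They are not: section 9.5.1 summarises all AEs, and the protocol ties no table to treatment-emergent status. What is lost is a label.

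A third tempting inference is a material bias towards no difference between arms. The rule is the same in both arms and the safety analysis is descriptive. Equal proportional loss leaves a risk ratio about unchanged and shrinks an absolute difference by the same fraction. Reversal has its own dilution, because titration events would be counted in both arms. It is therefore a trade-off, though in the cautious direction.

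**Conclusion.** The point holds as a badly chosen default with an undefined standard of proof. The protocol fixes the rule itself, so this is not a detail left to the SAP.

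On date parts alone, Rule 1 withholds the label from day-missing AEs in the randomisation month and from year-only AEs in the randomisation year. For day-missing AEs that is about 4% of the 52 weeks but about half of the first 28 days after the switch. For year-only AEs it is about half of the 52 weeks. These shares rest on uniform randomisation dates and a constant AE rate.

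The effect on all AEs is probably small and similar in both arms. The 5% upper figure needs one AE in ten to be partially dated and nearly all of those to lack the month. Such year-only events would also be spread over the rest of the randomisation year, not gathered just after the switch. The reason to act is that the affected window is the one of most interest and the repair is cheap.

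**What to change.** In section 9.2.1, reverse the default: an AE with an incomplete start date is treatment emergent unless the known part of its start date, its stop date or visit records show onset before randomisation. Keep the existing start-date imputation, whose randomisation-date branch then has cases. State that the same default applies when the month is unknown.

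The cost is a short wording change. Treatment-emergent counts will rise somewhat. Some events that began during EPREX titration in the randomisation month (or year, if the month is unknown) will be counted as treatment emergent in both arms; stop dates and visit records will remove part of these.
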